**ALIVE Study** 

Table 2. Final sample size calculation taking into account 10% lost-to-follow-up

	Pha	ase II		PHASE III	PHASE II/III
		N total		N total	
		Phase		Phase	
Group	N	ll 	N	III 	N total
Trichuris trichiura					
ALB	23	26	93	103	129
FDCx1	45	50	178	198	248
FDCx3	45	50	178	198	248
Total	113	126	449	499	625
Strongyloides.					
stercoralis					
ALB			42	47	47
FDCx1			108	120	120
FDCx3			107	119	119
Total		0	257	286	286
Hookworm					
ALB			91	101	101
FDCx1			91	101	101
FDCx3			99	110	110
Total		0	281	312	312
TOTAL		126		1097	1223

<sup>1Calculated by inflating the sample size using considering 10% lost-to-follow-up

# 9.3 ANALYSES POPULATIONS

- Intention-to-Treat (ITT) population: defined as all randomized participants with valid informed consent.
- Modified Intention-to-Treat population: defined as all participants who took at least one dose of study intervention and/or have some particular amount of follow-up outcome data.
- Safety population: defined as the subset of participants for whom safety analyses will be conducted (e.g., participants who took at least one dose of study intervention).

Version 4.0

21st January 2022

**ALIVE Study** 

- Per-Protocol population: defined as a subset of the participants in the full analysis (ITT) set where participants with major protocol deviations will be excluded.
- Sensitivity analysis populations (if needed)

#### 9.4 DATA MANAGEMENT

Each trial site will be responsible for the internal quality management of study conduct, data and biological specimen collection, documentation and accurate CRF completion. A data management plan will be developed for each site. Any change the site-specific data management plan will be reported to the Sponsor.

Participant data will be collected using electronic CRF. Laboratory results will be recorded in adhoc database at each site. All data storage will be encrypted and password protected.

A Data Transfer Agreement will be established between the Sponsor and Study sites.

## 9.5 STATISTICAL ANALYSES

#### 9.5.1 GENERAL APPROACH

A Statistical Analysis Plan (SAP) for the trial will be developed. Two interim efficacy analyses are planned:
1) after the end of the phase II component for decision making to move to the phase III component; 2) after 50% of the study participants are enrolled. Regular evaluation of the safety data every 3 months will be performed by the DSMB. The study is designed as a superiority trial, so all tests will be two-sided and all statistical significance will be declared at the 0.05 level. Analysis will be done using R.

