## Rationale for the adaptive design

Adaptive clinical trial designs are based on the considerations that this design can make clinical trials more flexible and often more efficient, informative and they make better use of resources without lowering scientific and regulatory standards. Traditional or conventional clinical trials are run in three steps: design of the trial, conduct of the trial as per the design and finally data analyses according to a pre-specified analysis plan.

Version 4.0

ALIVE Study 21st January 2022

The proposed design comprises of firstly a phase II trial to evaluate safety and pharmacokinetics of the FDC. After analysis of the phase II component and conditional to the conclusions, the phase III component will be executed in the groups that best tolerate the FDC and this aligns with the flexible approach offered in adaptive trials such that changes can be made to the trial when necessary during the course of the trial.

An interim safety analysis will be performed before moving to phase III component to ensure safety of the dosage. The final analysis will take into account all the available data in the phase II and III components. An independent DSMB will analyse the data and suggest modifications for the trial in the event that the high doses of IVM are shown not to be safe.

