**ALIVE Study** 

21st January 2022

pending review by the DSMB. This is equivalent to 12 safety events which meet these criteria in 612 subjects recruited at the point of the interim analysis.

Efficacy evaluation: Anti-helminthic primary efficacy, measured by cure rate will be determined by analysing a stool sample taken 21(+/-7) days after completing treatment with Kato Katz, Baermann and PCR. (18,40). Cure is defined as absence of the species of STH in participants who had a positive egg count and/or larva for that STH at baseline. Cure rate (CR) is defined as the proportion of individuals cured (absence of any egg) to the total of those infected at baseline with each particular species of STH.

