### 10.1.2 STUDY DISCONTINUATION AND CLOSURE

This study may be temporarily suspended or prematurely terminated if there is sufficient reasonable cause to do so. Written notification, documenting the reason for study suspension or termination, will be provided to study participants, study physician, funding agency and regulatory authorities. If the study is prematurely terminated or suspended, the study physician will promptly inform study participants, the IRB/EC and will provide the reason(s) for the termination or suspension. Study participants will be contacted, as applicable, and be informed of changes to study visit schedule.

Circumstances that may warrant termination or suspension include, but are not limited to:

- Determination of unexpected, significant, or unacceptable risk to participants
- Demonstration of efficacy that would warrant stopping
- Insufficient compliance to protocol requirements
- Data that are not sufficiently complete and/or evaluable
- Determination that the primary endpoint has been met
- Determination of futility

Study may resume once concerns about safety, protocol compliance, and data quality are addressed and approved by the regulatory authorities.

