5.7 Interim analyses

Two interim analyses are planned: 1) after the end of the phase II component for decision making to move to the phase III component; 2) after 50% of the study participants are enrolled. Regular evaluation of the safety data every 3 months will be performed by the DSMB. The study is designed as a superiority trial, so all tests will be two-sided and an overall significance level will be 0.05 In the interim efficacy analysis, the expense function alpha with the O'Brien-Fleming approach will be used to determine the type I error rate for each interim and final analysis.

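### Protocol 9.5.1 tests everything at 0.05 with no allowance for repeated looks, while SAP 5.7 spends an overall 0.05 by O'Brien-Fleming; the two rules need to be aligned

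*Protocol*

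**What the plan says.** **Protocol 9.5.1.** "Two interim efficacy analyses are planned": the first "after the end of the phase II component for decision making to move to the phase III component", the second "2) after 50% of the study participants are enrolled". The same paragraph then says "all tests will be two-sided and all statistical significance will be declared at the 0.05 level". It gives no overall level, spending function or interim boundary. It also says that a SAP will be developed.

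**SAP 5.7.** The two interim times are the same, but they are no longer both labelled as efficacy analyses, and 0.05 becomes the overall two-sided level. "In the interim efficacy analysis, the expense function alpha with the O'Brien-Fleming approach will be used" to set the error rate at each interim and at the final analysis.

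**Whether the first look tests efficacy.** Protocol 9.5.1 says so. Protocol 2.2 (rationale for the adaptive design) says "An interim safety analysis will be performed before moving to phase III component to ensure safety of the dosage", and the synopsis entry on study duration also calls it a decision on safety.

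**When the second look falls.** Protocol 9.5.1 and SAP 5.7 put it at half of all participants. The stopping rules in Protocol section 3 give the count: "12 safety events which meet these criteria in 612 subjects recruited at the point of the interim analysis". The synopsis puts the efficacy look half-way through phase III.

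**Early stopping.** Protocol 10.1.2 lists "Demonstration of efficacy that would warrant stopping" among the circumstances that may end or suspend the study, without a boundary. Protocol 4.1 sends the reader for interim details to a Section 9.4.6. That section does not exist; 9.4 is Data Management.

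**The concern.** The primary cure-rate test has two different significance levels at the same look, depending on which document is open. The protocol's only stated rule covers all tests, stands in the paragraph that plans the interims, and makes no exception for them. Applied as written, it tests the accumulating T. trichiura data more than once at the full 0.05, which inflates the chance of a false claim of superiority. The SAP rule does not. Protocol 2.1 says the trial is meant to support WHO pre-qualification and registration, so the error rate of the primary claim should not depend on which document is read.

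This concerns alpha across looks. Alpha across arm pairs is a separate matter: the sample size uses 0.0167 per pair, while SAP 5.4.4 applies no adjustment.

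**Working it through.** **1. The plan's own figures.** The documents print no interim boundary, so the only related figures to reproduce are the T. trichiura powers. Inputs (Protocol 9.2, Table 1): cure rates 0.237, 0.437 and 0.59; n = 116, 223 and 223; two-sided alpha 0.05/3 = 0.0167. With pooled variance,

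power = Φ{ [|p1 − p2| − z(1 − α/2) × √(p̄(1 − p̄)(1/n1 + 1/n2))] / √(p1(1 − p1)/n1 + p2(1 − p2)/n2) }.

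For FDC against FDCx3 the difference is 0.153, z is 2.394, the pooled SE 0.0473 and the unpooled SE 0.0468. The argument is (0.153 − 0.1133)/0.0468 = 0.85, so power is 80.2% (stated 80%). The other two pairs give 90.6% (stated 91%) and 100% (stated 100%). The sample size therefore uses 0.05/3, with nothing set aside for interim looks.

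**2. T. trichiura information at each look.** Inputs: 625 T. trichiura participants, of whom 126 in phase II and 499 in phase III; 1,097 in phase III overall; 612 recruited at the second interim.

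- End of phase II: 126/625 = 0.20.
- Half of the participants, taken as half of the information: 0.50.
- 612 recruited, assuming that phase III enrols the species in proportion: (126 + 486 × 499/1097)/625 = (126 + 221)/625 = 0.56.
- Half-way through phase III (synopsis), same assumption: (126 + 249.5)/625 = 0.60.

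**3. Protocol rule, read literally.** Each look uses |Z| > 1.96, and the statistics at two looks have correlation √(t1/t2). For one interim at t plus the final, type I error = 1 − P(|Z1| < 1.96, |Z2| < 1.96).

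| Looks (information) | Type I error, one comparison |
|---|---|
| 0.50, 1 | 8.3% |
| 0.56, 1 | 8.1% |
| 0.60, 1 | 8.0% |
| 0.20, 0.50, 1 | 11.7% |

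**4. SAP rule.** The Lan-DeMets O'Brien-Fleming-type function with 0.025 per side spends α(t) = 4[1 − Φ(2.2414/√t)]. At t = 0.50: 2.2414/0.7071 = 3.170, the tail is 0.00076, and four times that is 0.00305. The final level is solved so that the total is 0.05.

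| Interim at | Interim nominal p | Final nominal p |
|---|---|---|
| 0.50 | 0.0031 | 0.049 |
| 0.56 | 0.0053 | 0.048 |
| 0.60 | 0.0077 | 0.048 |

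An additional look at 0.20 would have a nominal level of about 0.000001 and would leave the later levels unchanged to the digits shown.

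**5. Sensitivity to the O'Brien-Fleming form.** SAP 5.7 does not say which version it means. At t = 0.50 the classical boundary gives 0.0052 and 0.048; the spending function applied directly to two-sided 0.05 gives 0.0056 and 0.048. At t = 0.60 that last form gives about 0.011 and 0.046.

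**6. Where the documents part.** An interim p of 0.02 meets the protocol's level and fails the SAP's under every version above. A final p of 0.0495 is also split.

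**The case against.** The strongest reply is that the SAP has already dealt with this. Protocol 9.5.1 announces a SAP, and SAP 5.7 repeats that paragraph almost point by point, turns 0.05 into the overall level and adds the spending function. It reads as a later document completing a general statement. That is a fair account of the likely intention. But the protocol does not delegate the significance level; it fixes one. The SAP does not say that it replaces the protocol text, so the mismatch stands.

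Three stronger readings are tempting, and the documents do not support them:

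- **The false-positive rate more than doubles.** That needs an efficacy test at the end of phase II (11.7%). Protocol 9.5.1 labels that look as efficacy, but the synopsis and section 2.2 make it a safety decision. With one efficacy look the figure is about 8%.
- **An interim p below 0.05 wins the trial under the protocol.** No passage says that success is declared at an interim. Section 10.1.2 is a general list of circumstances, with no boundary. What differs is the significance level.
- **The protocol governs and carries the wrong rule.** Neither document states which one prevails.

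It is also fair to object to a single interim threshold of 0.003. It holds only for 50% T. trichiura information and one version of the spending function, so a range has to be given.

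**Conclusion.** The conflict is real and stands in the current text of both documents. Followed literally, Protocol 9.5.1 gives a type I error of about 8% per comparison with one phase III efficacy look plus the final, against 5% under SAP 5.7. The figure of 11.7% applies only if the end-of-phase-II look also tests efficacy, and on that the documents disagree.

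Under the usual Lan-DeMets form, the split region is an interim p from roughly 0.003-0.008 up to 0.05 and a final p from about 0.048-0.049 up to 0.05. Other O'Brien-Fleming versions raise the interim edge to at most about 0.011 and lower the final edge to about 0.046. The conflict remains in every variant; only the edges move.

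The information fractions of 0.56 and 0.60 assume that phase III enrols the species in proportion, that each participant is counted under one species, and that those recruited have their day-21 result. All figures are for one comparison at two-sided 0.05. The point should be fixed because the error-rate consequence is material and the remedy is almost entirely wording.

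**What to change.** Amend Protocol 9.5.1 to say that 0.05 is the overall two-sided level and that it is spent by the O'Brien-Fleming function of SAP 5.7 over the phase III interim and final analyses of the primary endpoint. In addition:

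- State that the end-of-phase-II analysis serves the safety decision and makes no confirmatory efficacy claim. The planned phase II cure-rate and egg-reduction summaries can stay as descriptive results. If the sponsor does intend an efficacy test there, include that look in the spending.
- Reconcile the interim timing in the synopsis (half-way through phase III) with that in 9.5.1 (half of all participants).
- State the T. trichiura information fraction at the interim, the O'Brien-Fleming version used, and the resulting nominal levels.
- Make the reference to each interim in SAP 5.7 match the number of looks that test efficacy.
- Correct the pointer in Protocol 4.1 to the non-existent Section 9.4.6.

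The cost is wording in both documents. The final nominal level falls from 0.05 to about 0.048-0.049 under the usual spending form. How alpha is shared across the arm pairs has to be settled separately, and the nominal levels recalculated if it changes.

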# 9.5.2 ANALYSIS OF THE PRIMARY ENDPOINT(S)

The primary safety endpoints in phase II, are the frequency, type, severity and relationship to study drug for all adverse events and severe adverse events.

The primary efficacy endpoints for the efficacy phase III trial the cure rates for *T. trichiura* and 21 days after treatment using microscopy. Cochran–Mantel–Haenszel (CMH) test, controlling the effect of site if that is appropriate (sufficient participants), will be used to compare the cure rates for the 3 treatment

Version 4.0

**ALIVE Study** 

21st January 2022

groups. A participant is considered cured if the baseline egg count or larval count is not 0 while the post-treatment egg count or larval count is 0.

A total of 2 stool samples (1 pre-treatment and 1 post-treatment) will be obtained from each participant. The primary efficacy analysis will be based on ITT population. Efficacy for each type of infection will be analysed separately. A participant with multiple infections will be included in the analysis of each target species that the participant is infected with.

Stool sample collected pre-treatment will be used for the baseline information, and stool sample collected post-treatment will be used for the post-treatment information in the statistical analysis.

# **Pharmacokinetic parameters**

FDC concentrations (Cmax), time to reach Cmax (Tmax) and area under the curve (AUC). For the pharmacokinetic analysis, PK parameters will be obtained by non-compartmental analysis using WinNonlin (5.2, Certara, Princeton, NJ, USA). Maximum FDC concentrations (Cmax) and time to reach Cmax (Tmax) will be observed values. The half-life (the time in which half of the absorbed drug is eliminated) will be calculated as t1/2"In(2)/kZ. AUC was determined until the last measurement (AUCO—72) and until infinity (AUCINF).

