# **Secondary Endpoints:**

- 1. Measurement of Cure Rate (CR) for *T. trichiura* after the different treatment arms
- 2. Measurement of the Egg Reduction Rate (ERR) for *T. trichiura* after the different treatment arms
- 3. Measurement of CR for hookworm and *S. stercoralis* in those coinfected with species concomitantly to their infections with *T. trichiura*.

Version 4.0

ALIVE Study 21st January 2022

- 4. Measurement of ERR for hookworm in those co-infected with species concomitantly to their infections with *T. trichiura*.
- 5. Measurement of the rate of absorption (Cmax), time to reach Cmax (Tmax) and extent of absorption (AUC) of the FDC and FDCx3.
- Participant acceptability/palatability evaluation of the FDC 400mg-18mg and 400mg-9mg using the 5 point Likert/numeric rating scale (NRS).

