# Secondary outcome measures

**Treatment efficacy:** Anti-helminthic efficacy, measured through egg reduction rate (ERR), will be determined by analysing a stool sample taken 21(+/-7) days after completing treatment with Kato Katz, Baermann and PCR (40). Egg reduction rate (ERR) will be calculated by using geometric means, calculated for hookworms, *T. trichiura* and *A. lumbricoides*.

At pre- and post-treatment visits a duplicate Kato-Katz test will be performed on a fresh stool sample collected <24 hours before examination. Baermann method will also be performed in parallel to Kato-Katz for the search of *S. stercoralis*. Evaluation by PCR will be performed in pre- and post-treatment samples.

**Pharmacokinetic outcome measures:** Two blood samples for population PK analysis will be collected for every participant by finger prick using the mitra devices (41) in the phase II component to cover the following timepoints to determine FDC concentrations (Cmax), time to reach Cmax (Tmax) and area under the curve (AUC):

- ALB arm: 1, 2, 3, 4, 5, 6, 7, 8, 24h after treatment administration.
- FDC Single dose arm: 1, 2, 3, 4, 5, 6, 7, 8, 24, 48, 72h after treatment administration.
- FDC Three-day arm: 1, 2, 3, 4, 5, 6, 7, 8, 24, 48, 72h after treatment administration (time points considered respective to the last dose on Day 2). In this group, 1 additional timepoint will be collected at Day 2 pre-dose.

Refer to Section 8.2 for additional information on population PK.

Version 4.0 21st January 2022

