8.2 SAFETY AND OTHER ASSESSMENTS

Study procedures are specified in the SOA. The Site PI or delegated study physician will observe each participant for 3h after drug administration. A symptom-directed (targeted) physical examination will be performed at screening and when needed to evaluate possible adverse event(s) (i.e. any new symptoms). No physical exam is needed for routine study visits.

Pharmacokinetic Assessments (Phase II component only at Kenya)

Pharmacokinetic (PK) assessments will be conducted in participants in the three arms of the phase II trial (only Kenya). PK sampling (2 timepoints per participants in arm 1 and 2, 3 timepoints for arm 3) will be performed by finger prick using Mitra(40) Clamshell Devices. The 126 subjects included in the 3 arms of treatment will be randomly assigned to 7 subgroups (for arm 1) and 10 subgroups (for arm 2 and 3) with different sampling times (2 blood samples per subgroup) that will be extracted from all the participants.

Version 4.0

21st January 2022

ALIVE Study

The two sampling times are obtained from two different post-dosing ranges covering from 1 to 7 hours (range I) and from 8 to 72 hours (range II). Thus, the overall sampling times describes the entire pharmacokinetic profile for the two drugs (Ivermectine and Albendazole) for each of the 3 groups of body

PK blood sampling (2 timepoints per participant) will cover the following timepoints:

- Albendazole arm: 1, 2, 3, 4, 5, 6, 7, 8 and 24h after treatment administration.
- Single dose FDC arm: 1, 2, 3, 4, 5, 6, 7, 8, 24, 48 and 72 h after treatment administration
- Three-day FDC arm: 1, 2, 3, 4, 5, 6, 7, 8, 24, 48 and 72 h after treatment administration (time points considered respective to the last dose on day 2). For this arm, 1 additional timepoint will be collected for all participants at pre-dose Day 2.

PK data generated during the phase II component will be analysed according to the Statistical Analysis Plan.

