2.1.1.2 Secondary objectives

- 1. To evaluate the efficacy of FDC against *T. trichiura* in paediatric population.
- 2. To evaluate the efficacy of FDC against hookworms and *S. stercoralis* in those co-infected with species concomitantly to their infections with *T. trichiura*.
- 3. To describe the extent of albendazole and ivermectin exposure in different weight strata.
- 4. To evaluate the acceptability/palatability of the FDC 400mg-18mg and 400mg-9mg.

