²⁵ Treatment Day 2. Only for participants in treatment Arm 3. Close observation for 3 hours post-treatment for safety evaluations.

²⁶ Adverse events will be assessed by direct observations of the study physician, or reported by the participant or parent/guardian.

rate will be determined by analysing a stool sample taken 21(+/-7) days after completing treatment with qPCR.

At pre- and post-treatment visits a duplicate Kato-Katz test will be performed on a fresh stool sample collected <24 hours before examination. Baermann method will also be performed in parallel to Kato-Katz for the search of *S. stercoralis*. Evaluation by qPCR will be performed in pre- and post-treatment samples.

Pharmacokinetic outcome measures (only phase II): Two blood samples for population PK analysis will be collected for every participant by finger prick using the mitra devices [3] in the phase II component to adjust a population pharmacokinetic model. Additionally, a NCA will be performed to obtain (Cmax), time to reach Cmax (Tmax) and area under the curve (AUC) of ALB and IVM. A complete description of the pk analysis can be found in the statistical analysis plan for pharmacokinetics.

Participant acceptability/palatability outcome measures (only phase II):

Facial hedonic scale and implied numerical rating scale (NRS) will be included in the Phase II component of the trial to measure attributes for the FDC orodispersible formulation in terms of taste, aftertaste; mouth feel; smell; time needed to dissolve/disperse (duration of administration). Secondary aspects will include visual aspects: embossing, surface aspects and colour. Refer to the protocol Section 9.5.2 for details.

Resistance: Whole genome sequencing, next-generation DNA sequencing and omic approaches will be used to assess underlying factors associated with low treatment response including assessment and evaluation of new protocols for sample processing and sequencing.

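### Does Protocol 9.5.2 need changing because it describes only non-compartmental PK analysis while each child gives two post-dose samples?

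*Protocol*

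**What the plan says.** **Protocol 9.5.2, Pharmacokinetic parameters.** The method is that "PK parameters will be obtained by non-compartmental analysis using WinNonlin". It adds that "Maximum FDC concentrations (Cmax) and time to reach Cmax (Tmax) will be observed values", takes half-life from the terminal slope, and says "AUC was determined until the last measurement" (labelled 0-72 h) and also to infinity. It mentions no population model and does not say whether the unit is the child or a pooled profile.

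**Protocol 1.1, Phase II secondary endpoint 5.** "Measurement of the rate of absorption (Cmax), time to reach Cmax (Tmax) and extent of absorption (AUC) of the FDC and FDCx3". The endpoint names the two FDC regimens, not the albendazole (ALB) arm.

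**Protocol 3, Secondary outcome measures.** "Two blood samples for population PK analysis will be collected for every participant by finger prick using the mitra devices". FDCx3 children also give a pre-dose sample on Day 2.

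**Protocol 8.2.** "PK data generated during the phase II component will be analysed according to the Statistical Analysis Plan". The section also says that the sampling times together trace each drug's full curve in each of the three weight groups.

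**SAP.** One Phase II objective is "To describe the extent of albendazole and ivermectin exposure in different weight strata". Section 2.2.2 collects the samples "in the phase II component to adjust a population pharmacokinetic model" and adds an NCA for Cmax, Tmax and AUC of both drugs. Section 4.1 lists the slots and repeats that they jointly describe the curve by weight group. Sections 2.2.2 and 4.1 place the full description in a separate PK analysis plan, and section 5.6.1 reports the population PK analysis in a separate document.

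**The concern.** Observed Cmax and Tmax, a terminal slope, and AUC to 72 h and to infinity are what one reports when every subject has a full concentration curve. Here no child has more than two post-dose samples. Read child by child, Tmax could only be one of two preassigned hours, AUC to the last sample would depend on whether that sample fell at 7 h or 72 h, and an individual half-life could not be estimated properly. In the ALB arm nobody is sampled after 24 h, so a 0-72 h label has no meaning there.

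The two documents also differ in emphasis: 9.5.2 names NCA only, while the SAP leads with a population model. If the choice of method and unit stayed open, the same samples could give quite different exposure figures for the weight groups, and describing exposure by weight is a stated Phase II objective.

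**Working it through.** **1. Reproduce the plan's count.** From the subgroup lists in SAP 4.1: ALB arm 5 × 4 + 2 × 3 = 26; each FDC arm 10 × 5 = 50; total 26 + 50 + 50 = 126, as stated. The supplied text shows nine subgroups for the single-dose arm. The tenth (1 h and 24 h) is taken from the FDCx3 list, which the SAP says follows the same schedule.

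**2. What each child and each arm provides.**

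| | FDC arms (50 each) | ALB arm (26) |
|---|---|---|
| Post-dose samples per child | 2 | 2 |
| Last sample at 72 h | 10 | 0 |
| Last sample at 24 h or later | 30 | 7 |
| Last sample at 6-8 h | 20 | 19 |
| Children at each sampled hour, pooled | 10 at each of 1, 2, 3, 4, 5, 7, 8, 24, 48, 72 h | 4 to 8 at each of 1-8 and 24 h |

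A single child cannot support a terminal fit. A pooled FDC profile has ten time points, three of them (24, 48 and 72 h) late.

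**3. Per child against pooled.** The documents give no kinetics, so these are assumptions: identical children and a one-compartment oral curve C(t) = [ka/(ka − k)](e^(−kt) − e^(−ka·t)), where k = ln 2 / half-life and ka is set by Tmax. Slower analyte: Tmax 3-5 h, half-life 12-36 h. Faster analyte: Tmax 2-5 h, half-life 4-8 h. Each AUC is divided by the exact value. Protocol 9.5.2 names no integration rule, so two are shown. Slots are those of the single-dose FDC arm.

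| AUC as % of true 0-72 h | Linear trapezoid | Linear up, log down |
|---|---|---|
| Per child, slower | 11-181 | 11-97 |
| Per child, faster | 25-413 | 25-91 |
| Pooled, slower | 101-106 | 99-100 |
| Pooled, faster | 110-119 | 95-99 |

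Per child, the second sample is not below the first (no positive terminal slope) in 5-20 of 50 children for the slower analyte and 0-15 of 50 for the faster one, whichever rule is used. Cmax suffers less: averaged over slots, the larger of a child's samples is 86-97% of the true peak in the FDC arms.

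So the unit matters a great deal, while the pooled result is serviceable under either rule. The very high per-child maxima (181% and 413%) and the pooled overestimate come from the linear rule, which the plan does not specify.

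**4. By weight group.** Expected children per FDC arm: 38 × 0.4 ≈ 15, 38 × 0.4 ≈ 15 and 50 × 0.4 = 20. Samples per hour: 15 × 2 / 10 = 3, and 20 × 2 / 10 = 4. If slots are not balanced within weight group, some hour has fewer than two children with probability 75% at n = 15 (27% at n = 20), and some hour has none with probability 16% (3%). With Tmax 4 h and half-life 24 h, a pooled group AUC at n = 15 has an SD of 10%, 17% or 26% for an assumed between-child CV of 30%, 50% or 80%.

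ALB arm: 38 × 0.2 ≈ 8 children give 16 samples over 9 hours, short of the 18 needed for two per hour. The group of 10 gives 20, so two per hour is possible there, and the whole arm has at least 4 at every hour.

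Pooled NCA by weight group is therefore thin. A population model does not need every hour filled within a group, because it fits all children together, and that model is already in SAP 2.2.2.

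**5. The passages together.** Protocol 9.5.2 names NCA and no unit. Protocol 3 labels the samples as population PK. Protocol 8.2 refers the analysis to the SAP. The SAP fits the model, keeps NCA as an addition and refers detail to the PK plan. Protocol 8.2 and SAP 4.1 both treat the slots as one joint profile. None of them asks for a parameter from each child.

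**The case for a change.** The strongest case for a change is that 9.5.2 is current text, that it does not match the sampling in the same protocol version, and that one sentence would settle the matter at almost no cost. Saying that the slots jointly cover the curve describes sampling and does not fix the NCA unit. The PK plan cannot be seen, so its content cannot be assumed. Half-life and AUC to infinity are named without qualification.

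Much of this stands. The paragraph is out of step with the rest of the plan, and the unit is not stated in the two documents. The consequence is weaker. The SAP retains NCA, so 9.5.2 is incomplete rather than contradicted. The damaging figures need a per-child reading that no passage states and that the design descriptions speak against.

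The ALB-arm point is also limited. Endpoint 5 covers FDC and FDCx3, and 9.5.2 speaks of FDC concentrations. Albendazole exposure can be described from the FDC arms, and an ALB-arm profile to its last measurement simply stops at 24 h. Rewriting 9.5.2 around the population model would mostly restate what SAP 2.2.2 already plans.

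**Conclusion.** No change to the plan is needed. What remains is one paragraph that omits the population model and a missing statement of the NCA unit. An analyst with two samples per child, a planned population model and a separate PK plan would take exposure by weight group from the model and run the NCA on pooled profiles.

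On that reading, the pooled FDC AUC to 72 h lies within 95-119% of the true value across both integration rules and all the assumed kinetics. Precision by weight group is modest, which is a property of the sparse design that new wording would not improve. The endpoint is descriptive, secondary and confined to Phase II. Under Protocol 4.1, clearance to proceed to Phase III rests on safety data, and the Phase III *T. trichiura* cure-rate analysis uses none of these figures.

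The conclusion rests on two assumptions: that the NCA is pooled, as Protocol 8.2 and SAP 4.1 suggest, and that one-compartment curves are a fair guide to the size of the error. If the PK plan did prescribe NCA child by child, the individual AUC, Tmax and half-life values would largely reflect slot assignment and should not be used to describe exposure.
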